7.3 Concomitant medications

Concomitant medications will be recorded at screening and at every visit during the treatment phase of the study in the case report form (CRF) in the concomitant therapy section.

7.3.1 Prohibited Concomitant Medications

Medications or vaccinations specifically prohibited in the exclusion criteria are also not allowed during the ongoing trial. If there is a clinical indication for one of these or other prohibited medications or vaccinations then the patient may be discontinued from trial therapy. The Investigator should discuss any questions regarding this with the Chief Investigator or delegate.

The final decision on any supportive therapy or vaccination rests with the Investigator and/or the patient's primary physician. However, the decision to continue the patient on trial therapy or vaccination schedule requires the mutual agreement of the Chief Investigator, and the patient.

Patients are prohibited from receiving the following therapies during the Screening and Treatment Phase of this trial:

- Anti-cancer systemic chemotherapy or biological therapy
- Immunotherapy not specified in this protocol
- Investigational agents other than pembrolizumab
- Live vaccines within 30 days prior to the first dose of trial treatment, while participating in the trial and within the first 3 months after the last dose of study treatment. Examples of live vaccines include, but are not limited to, the following: measles, mumps, rubella, chicken pox, yellow fever, rabies, BCG, and typhoid (oral) vaccine. Seasonal influenza vaccines for injection are generally killed virus vaccines

and are allowed; however intra-nasal influenza vaccines (e.g. Flu-Mist®) are live attenuated vaccines, and are not allowed.

- Glucocorticoids for any purpose other than to modulate symptoms from an event of clinical interest of suspected immunologic aetiology. The use of physiologic doses of corticosteroids may be approved after consultation with the Chief Investigator or delegate.
- Radiotherapy not specified in this protocol:
 - Note: Subsequent radiotherapy whilst on maintenance treatment to the thorax will not be permitted. Radiation therapy to a symptomatic solitary lesion or to the brain may be allowed after consultation with the chief investigator, as long as it does not involve re-irradiation to any part of the lung.

Patients who in the assessment by the Investigator, requires the use of any of the aforementioned for their clinical management should be removed from the trial. Patients may receive other medications that the investigator deems to be medically necessary. The Exclusion Criteria describes other medications, which are prohibited in this trial. There are no prohibited therapies during the Post-Treatment Follow-up Phase.

7.3.2 Acceptable Concomitant Medications

All treatments that the Investigator considers necessary for a patient's welfare may be administered at the discretion of the Investigator in keeping with the community standards of medical care. All concomitant medication will be recorded on the case report form (CRF) including all prescriptions, over-the-counter (OTC), herbal supplements, and i.v. medications and fluids. If changes occur during the trial period, documentation of drug dosage, frequency, route, and date may also be included on the CRF.

All concomitant medications received within 28 days before the first dose of trial treatment and 30 days after the last dose of trial treatment or initiation of other anti-cancer therapies should be recorded. Concomitant medications administered after 30 days after the last dose of trial treatment should only be recorded for SAEs and overdose and liver toxicity ECIs as defined in Section 8.

7.4 Rescue Medications & Supportive Care

7.4.1 Supportive Care Guidelines

Patients should receive appropriate supportive care measures as deemed necessary by the treating investigator including but not limited to the items outlined below:

7.4.1.1 Diarrhoea

Patients should be carefully monitored for signs and symptoms of:

- Enterocolitis (diarrhoea, abdominal pain, blood or mucus in stool, with or without fever)

- Bowel perforation (peritoneal signs and ileus).

In symptomatic patients, infectious aetiologies should be ruled out, and if symptoms are persistent and/or severe, endoscopic evaluation should be considered.

- In patients with severe enterocolitis (Grade 4):

- Pembrolizumab will be **permanently discontinued** and treatment with systemic corticosteroids should be initiated at a dose of 1 to 2 mg/kg/day of prednisone or equivalent. If symptoms are not improving within 48 hours, consider infliximab. When symptoms improve to Grade 1 or less, corticosteroid taper should be started and continued over at least 1 month.

- In patients with moderate enterocolitis (Grade 2-3):

- Pembrolizumab should be **withheld** and anti-diarrhoeal treatment should be started. If symptoms are persistent for more than one week, systemic corticosteroids should be initiated (e.g., 0.5 mg/kg/day of prednisone or equivalent). If symptoms are not improving within 48 hours of starting steroids for grade 3 enterocolitis, consider infliximab. When symptoms improve to Grade 1 or less, corticosteroid taper should be started and continued over at least 1 month. Guidelines for continuing treatment with pembrolizumab can be found in Appendix 5.

All patients who experience diarrhoea should be advised to drink liberal quantities of clear fluids. If sufficient oral fluid intake is not feasible, fluid and electrolytes should be substituted via i.v. infusion.

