Monitor subjects for signs and symptoms of colitis and exclude other causes of colitis. Administer corticosteroids for Grade 2 (if persists for >3 days) or greater events (initial dose of 1-2 mg/kg/day prednisone or equivalent followed by a taper), withhold pembrolizumab for moderate (Grade 2) or severe (Grade 3) colitis, and permanently discontinue pembrolizumab for life-threatening (Grade 4) colitis.

Immune-mediated hepatitis

Monitor subjects for changes in liver function (at the start of treatment, periodically during treatment and as indicated based on clinical evaluation) and symptoms of hepatitis, and exclude other causes of hepatitis. Administer corticosteroids (initial dose of 0.5 – 1.0 mg/kg/day for grade 2 events, and 1 – 2 mg/kg/day for grade 3 or greater events, of prednisone or equivalent, followed by a taper) and, based on severity of liver enzyme elevations, withhold or discontinue pembrolizumab.

Immune-mediated nephritis

Monitor patients for changes in renal function and exclude other causes of nephritis. Administer corticosteroids for grade 2 or greater events (initial dose of 1 – 2 mg/kg/day prednisone or equivalent, followed by a taper), withhold pembrolizumab for moderate (Grade 2), and permanently discontinue pembrolizumab for severe (Grade 3) or life-threatening (Grade 4) nephritis.

Immune-mediated endocrinopathies

Monitor subjects for signs and symptoms of hypophysitis (including hypopituitarism and secondary adrenal insufficiency) and exclude other causes of hypophysitis. Administer corticosteroids to treat secondary adrenal insufficiency and other hormone replacement as clinically indicated, withhold pembrolizumab for moderate (Grade 2), withhold or discontinue pembrolizumab for severe (Grade 3) or for life-threatening (Grade 4) hypophysitis.

Monitor subjects for hyperglycemia or other signs and symptoms of type 1 diabetes. Exclude other causes of diabetes. Administer insulin for type 1 diabetes, and withhold pembrolizumab in cases of severe hyperglycemia until metabolic control is achieved.

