	Grade 2 (For grade 2 diarrhoea that persists > 3 days)	
 Report overdose and liver toxicity ECIs within 24 hours Withhold pembrolizumab, may restart if Grade 1 or resolved within 12 weeks Symptomatic treatment 
 Consider GI consult & endoscopy to rule out colitis 	
 Prednisone 1-2mg/kg/day or equivalent Symptoms grade 1 or less, initiate steroid taper for no less than 4 weeks. Permanently discontinue pembrolizumab if dose cannot be reduced to 10mg or less of prednisone or equivalent per days within 12 weeks. If symptoms worsen or persist >1 week treat as grade 3.
--	---	--	--

	Grade 3	
 Withhold pembrolizumab Rule out bowel perforation Recommend gastroenterologist consult & biopsy with endoscopy 	
 methylprednisolone 125mg IV followed by prednisone 1 to 2 mg/kg/day or dexamethasone 4mg every 4 hours. Symptoms grade 1 or less initiate steroid taper for no less than 4 weeks. Taper 6-8 weeks in patients with diffuse or severe ulceration and/or bleeding If IV steroids do not reduce initial symptoms within 48-72 hours treat with additional anti-inflammatory measures. At symptom relief discontinue anti-inflammatory and initiate steroid taper over 45-60 days. If symptoms worsen during this period refer to Section 7 and 8.
	Grade 4	
 Discontinue pembrolizumab 	
 Manage as per grade 3
Endocrine – Hypo and hyperthyroidism	Grade 1 (Asymptomatic)	
 No action 	
 Intervention not indicated
	Grade 2 Hyperthyroidism and Grade 2- 4 Hypothyroidism	
 Monitor thyroid function until returned to baseline. Consider consultation with endocrinologist. Pembrolizumab can continue while on this treatment. 	
 Thyroid hormone and/or steroid replacement therapy. Hyper – non-selective beta blockers for initial therapy Hypo – thyroid hormone replacement therapy as per standard of care.

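### For grade 2-3 enterocolitis, section 7.4.1.1 prompts steroids later and at a lower dose than section 7.5 and Appendix 5, and nothing in the protocol says which prevails

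*Protocol*

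**What the plan says.** Three places in the protocol tell the clinician how to use steroids for bowel inflammation on pembrolizumab.

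- **Section 7.4.1.1 (Diarrhoea).** Grades 2 and 3 are handled together under the label moderate. Pembrolizumab is withheld and anti-diarrhoeal treatment is started. Then: "If symptoms are persistent for more than one week, systemic corticosteroids should be initiated (e.g., 0.5 mg/kg/day of prednisone or equivalent". The only reference to the appendix reads: "Guidelines for continuing treatment with pembrolizumab can be found in Appendix 5".
- **Section 7.5 (immune-mediated colitis).** "Administer corticosteroids for Grade 2 (if persists for >3 days) or greater events (initial dose of 1-2 mg/kg/day prednisone or equivalent". The grade labels differ from those in 7.4.1.1: "withhold pembrolizumab for moderate (Grade 2) or severe (Grade 3) colitis".
- **Appendix 5 (colitis rows).** The grade 2 row applies to diarrhoea persisting beyond 3 days and gives "Prednisone 1-2mg/kg/day or equivalent", adding "If symptoms worsen or persist >1 week treat as grade 3". The grade 3 row gives "methylprednisolone 125mg IV followed by prednisone 1 to 2 mg/kg/day or dexamethasone 4mg every 4 hours".

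**The concern.** Read literally, the three texts give different answers for the same patient. A clinician who opens the section called Diarrhoea for a patient with grade 2 or 3 enterocolitis is prompted to try anti-diarrhoeals first and to add a modest steroid dose only after a week. A clinician who opens 7.5 or Appendix 5 is prompted to start sooner and at a higher dose, intravenously first for grade 3 under Appendix 5.

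What is at stake is patient safety: possible late or weak treatment of an immune-mediated event in a phase I combination trial. There is also a consistency issue, because sites or individual clinicians could manage the same event differently while each follows the protocol.

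**Working it through.** The protocol states no figure to reproduce. The check is a side-by-side reading plus one dose ratio.

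**1. Are these the same events?** Yes. Section 7.4.1.1 is headed Diarrhoea, but it manages enterocolitis with pembrolizumab withholding, steroids and infliximab. Table 12 lists enterocolitis and diarrhoea in its colitis group. The grade 2 colitis row of Appendix 5 is itself triggered by diarrhoea. The texts cannot be reconciled as covering different conditions.

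**2. Steroid start and dose, by grade**

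| | 7.4.1.1 | 7.5 | Appendix 5 |
|---|---|---|---|
| Grade 2, trigger | more than one week | more than 3 days | more than 3 days |
| Grade 2, dose | 0.5 mg/kg/day (example) | 1-2 mg/kg/day | 1-2 mg/kg/day; treated as grade 3 if worse or beyond one week |
| Grade 3, trigger | more than one week | no wait stated | no wait stated |
| Grade 3, dose | 0.5 mg/kg/day (example) | 1-2 mg/kg/day | methylprednisolone 125 mg IV, then prednisone 1-2 mg/kg/day or dexamethasone |

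**3. Dose ratio (prednisone).** Lower end: 1 / 0.5 = 2. Upper end: 2 / 0.5 = 4. As an illustration, at an assumed 70 kg: 0.5 x 70 = 35 mg/day against 1 x 70 = 70 to 2 x 70 = 140 mg/day.

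**4. Grade 2 beyond one week.** Section 7.4.1.1 starts steroids here, at the example dose of 0.5 mg/kg/day. Appendix 5 moves to the grade 3 regimen, which starts intravenously. Neither place defines when its week begins. If the Appendix 5 week runs from the start of steroids and not from first symptoms, the two steps need not coincide. Even so, a patient managed under Appendix 5 would already have been on 1-2 mg/kg/day since passing 3 days.

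**5. Second-line timing.** Section 7.4.1.1 suggests infliximab if grade 3 has not improved within 48 hours of starting steroids. Appendix 5 adds further anti-inflammatory measures if intravenous steroids have not worked within 48-72 hours.

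**6. What agrees.** Withholding pembrolizumab at grades 2-3 is consistent across 7.4.1.1, 7.5, Appendix 5 and Table 8. Steroid tapers are essentially the same (at least a month against at least 4 weeks), apart from the 6-8 weeks in Appendix 5 for diffuse or severe ulceration or bleeding.

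**7. Does any text rank the three?** Section 7.5 sends drug-associated immune-related events of clinical interest to Appendix 5, but it does not say that Appendix 5 overrides 7.4.1.1, and it gives its own regimen without the intravenous start. The reference in 7.4.1.1 is limited to continuing pembrolizumab. No precedence rule was found.

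**The case against.** The strongest reply is that the protocol already leads the clinician to Appendix 5.

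- Section 6.3.2 refers adverse events of possible immunological cause to Appendix 5.
- Section 8.5.1 requires a check for such events before each dose and presumes an immune cause when no other is found.
- Table 12 classes diarrhoea, enterocolitis and colitis of grade 2 or higher as events of clinical interest, and 7.5 refers drug-associated ones to Appendix 5.
- Section 7.4.1 leaves supportive care to the treating investigator. Section 7.3.1 permits glucocorticoids for such events. Section 7.5 asks for immediate discussion of grade 2 or higher immune events with the Chief Investigator or a delegate.
- The dose in 7.4.1.1 is only an example, and that section can be read as general care while infection is excluded.
- Section 7.4.1.4 mentions a separate guidance document held at sites, which is not available here and may settle the matter in practice.

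Much of this stands. It means that earlier or stronger treatment is allowed and often signposted. It does not remove the conflict. The example wording softens the dose but not the one-week trigger, and routing to Appendix 5 from other sections does not cancel the instruction in 7.4.1.1. The Chief Investigator or delegate consulted would be reading the same conflicting text.

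A reader might infer three further points that the protocol does not support.

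- *A grade 4 conflict.* For grade 4, section 7.4.1.1 says "treatment with systemic corticosteroids should be initiated at a dose of 1 to 2 mg/kg/day of prednisone or equivalent". Section 7.5 gives the same dose, and the wording fixes no route. The intravenous start in Appendix 5 is added detail, not a contradiction.
- *A calculable delay in days.* The start of the week is undefined, and any count also depends on whether grade 2 came before grade 3. Only the stated triggers can be compared.
- *A colitis conflict with Table 10.* Section 7.5 reserves that table for immune events not covered elsewhere, so colitis falls outside it. The reference in 7.4.1.4 to a Section 6.5, which does not exist, is an editorial slip.

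**Conclusion.** The conflict is real for grades 2 and 3 and should be corrected. The documented differences are more than one week against more than 3 days (grade 2), more than one week against no stated wait (grade 3), and an example prednisone dose 2 to 4 times lower in 7.4.1.1. Appendix 5 adds an intravenous start for grade 3 that neither 7.4.1.1 nor 7.5 mentions.

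A reader might conclude that the protocol imposes a week's delay. It does not: earlier steroids would not be a breach, and several sections point to Appendix 5. The hazard is a conflicting prompt for someone who relies on 7.4.1.1 alone. How often that would happen cannot be judged from the protocol, particularly without the separate site guidance.

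Nor should the point be read as statistical. The dose-limiting toxicity definition in section 4.2.1 does not refer to steroid treatment, and no sample size or decision threshold depends on it.

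**What to change.** In section 7.4.1.1:

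- replace the grade 2-3 steroid trigger and dose with a reference to the colitis rows of Appendix 5;
- separate grade 3 from grade 2;
- align the timing of infliximab or other anti-inflammatory treatment (48 hours against 48-72 hours);
- state that Appendix 5 prevails for suspected immune-mediated enterocolitis.

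In section 7.5, add a cross-reference to the Appendix 5 intravenous regimen for grade 3 and above. The Section 6.5 reference in 7.4.1.4 can be corrected to 7.5 at the same time. The clinical team should confirm the content, and should check that the separate site guidance matches.

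The cost is a wording amendment through the approvals in section 11.7: trial management group, sponsor, ethics committee, the regulator where required, and local R&D. It needs no new data or procedures.

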7.4.1.2 Nausea/vomiting

Nausea and vomiting should be treated aggressively, and consideration should be given in subsequent cycles to the administration of prophylactic antiemetic therapy according to standard institutional practice. Patients should be strongly encouraged to maintain liberal oral fluid intake.

7.4.1.3 Infection

Patients with a documented infectious complication should receive oral or i.v. antibiotics or other anti-infective agents as considered appropriate by the treating investigator for a given infectious condition, according to standard institutional practice.

7.4.1.4 Immune-related adverse events

Please see Section 6.5 and Table 10 below and the separate guidance document in the administrative binder regarding diagnosis and management of adverse experiences of a potential immunologic aetiology.

7.4.1.5 Management of infusion reactions

Acute infusion reactions (which can include cytokine release syndrome, angioedema, or anaphylaxis) are different from allergic/hypersensitive reactions, although some of the manifestations are common to both AEs. Signs and symptoms usually develop during or shortly after drug infusion and generally resolve completely within 24 hours of completion of infusion. Signs/symptoms may include: Allergic reaction/hypersensitivity (including drug fever); Arthralgia (joint pain); Bronchospasm; Cough; Dizziness; Dyspnoea (shortness of breath); Fatigue (asthenia, lethargy, malaise); Headache; Hypertension; Hypotension; Myalgia (muscle pain); Nausea; Pruritus/itching; Rash/desquamation; Rigors/chills; Sweating (diaphoresis); Tachycardia; Tumour pain (onset or exacerbation of tumour pain due to treatment); Urticaria (hives, welts, wheals); Vomiting. Table 9 below shows treatment guidelines for patients who experience an infusion reaction associated with administration of pembrolizumab.

7.5 Supportive Care Guidelines for Immune-related Adverse Events (irAE) and Immune-related Events of Clinical Interest (irECI)

Immune-related Adverse Events (irAEs) may be defined as an AE of unknown aetiology, associated with drug exposure and is consistent with an immune phenomenon. irAEs may be predicted based on the nature of the pembrolizumab compound, its mechanism of action, and reported experience with immunotherapies that have a similar mechanism of action. Special attention should be paid to AEs that may be suggestive of potential irAEs. An irAE can occur shortly after the first dose or several months after the last dose of treatment. If an irAE is suspected, efforts should be made to rule out cancer, infectious, metabolic, toxin or other etiologic causes prior to labelling an AE as an irAE. Patients who develop a Grade 2 or higher irAE should be discussed immediately with the Chief Investigator or delegate.

Recommendations to managing irAEs not detailed elsewhere in the protocol are detailed in Table 10.

Table 9: Infusion Reaction Treatment Guidelines

CTCAE Grade	Treatment	Premedication at subsequent dosing
Grade 1 Mild reaction; infusion interruption not indicated; intervention not indicated	Increase monitoring of vital signs as medically indicated until the patient is deemed medically stable in the opinion of the investigator.	None
Grade 2 Requires infusion interruption but responds promptly to symptomatic treatment (e.g., antihistamines, NSAIDS, narcotics, IV fluids); prophylactic medications indicated for < =24 hrs	
Stop Infusion and monitor symptoms. Additional appropriate medical therapy may include but is not limited to:
 
 IV fluids Antihistamines NSAIDS Paracetamol Narcotics 
Increase monitoring of vital signs as medically indicated until the patient is deemed medically stable in the opinion of the investigator.
 
If symptoms resolve within one hour of stopping drug infusion, the infusion may be restarted at 50% of the original infusion rate (e.g. from 100 mL/hr to 50 mL/hr).
 
Otherwise dosing will be held until symptoms resolve and the patient should be pre-medicated for the next scheduled dose.
 
Patients who develop Grade 2 toxicity despite adequate premedication should be permanently discontinued from further trial treatment administration.
	
Patient may be pre-medicated 1.5h (± 30 minutes) prior to infusion of pembrolizumab with:
 
Diphenhydramine 50 mg p.o. (or equivalent dose of antihistamine).
 
Paracetamol 500-1000 mg p.o. (or equivalent dose of antipyretic).

Grades 3 or 4 Grade 3: Prolonged (i.e., not rapidly responsive to symptomatic medication and/or brief interruption of infusion); recurrence of symptoms following initial improvement; hospitalization indicated for other clinical sequelae (e.g., renal impairment, pulmonary infiltrates) Grade 4: Life-threatening; pressor or ventilatory support indicated	
Stop Infusion. Additional appropriate medical therapy may include but is not limited to:
 
 IV fluids Antihistamines NSAIDS Paracetamol Narcotics Oxygen Pressors Corticosteroids Epinephrine 
Increase monitoring of vital signs as medically indicated until the patient is deemed medically stable in the opinion of the investigator.
 
Hospitalization may be indicated.
 
Patient is permanently discontinued from further trial treatment administration.
	No subsequent dosing
Appropriate resuscitation equipment should be available in the room and a physician readily available during the period of drug administration. For Further information, please refer to the Common Terminology Criteria for Adverse Events version 5.0 (CTCAE) at http://ctep.cancer.gov		

Table 10: General Approach to Handling irAEs

irAE	Withhold/Discontinue Pembrolizumab?	Supportive Care
Grade 1	No action	Provide symptomatic treatment
Grade 2	May withhold pembrolizumab. For recurrent grade 2 pneumonitis, pembrolizumab should be discontinued permanently.	Consider systemic corticosteroids in addition to appropriate symptomatic treatment. Steroid taper should be considered once symptoms improve to Grade 1 or less and tapered over at least 4 weeks. Based on limited data from clinical studies in subjects whose immune-related adverse reactions could not be controlled with corticosteroid use, administration of other systemic immunosuppressants can be considered.
Grade 3 and Grade 4	Withhold pembrolizumab Discontinue if unable to reduce corticosteroid dose to < 10 mg per day prednisone equivalent within 12 weeks of toxicity	Systemic corticosteroids are indicated in addition to appropriate symptomatic treatment. May utilize 1 to 2 mg/kg prednisone or equivalent per day. Steroid taper should be considered once symptoms improve to Grade 1 or less and tapered over at least 4 weeks. Based on limited data from clinical studies in subjects whose immune-related adverse reactions could not be controlled with corticosteroid use, administration of other systemic immunosuppressants can be considered.
Please Note: If an irAE does not resolve or improve to \leq Grade 1 within 12 weeks after last administration of pembrolizumab, study therapy discontinuation should be considered after discussion with a Merck Clinical Director via the RM-CTU trial manager.		

Details for managing specific irAEs are summarised below:

Immune-mediated pneumonitis

Monitor subjects for signs and symptoms of pneumonitis. If pneumonitis is suspected, evaluate with radiographic imaging and exclude other causes. Administer corticosteroids for Grade 2 or greater events (initial dose of 1-2 mg/kg/day prednisone or equivalent followed by a taper), withhold pembrolizumab for moderate (Grade 2) pneumonitis, and permanently discontinue pembrolizumab for recurrent moderate (Grade 2), severe (Grade 3) or life-threatening (Grade 4) pneumonitis.

Immune-mediated colitis

Monitor subjects for signs and symptoms of colitis and exclude other causes of colitis. Administer corticosteroids for Grade 2 (if persists for >3 days) or greater events (initial dose of 1-2 mg/kg/day prednisone or equivalent followed by a taper), withhold pembrolizumab for moderate (Grade 2) or severe (Grade 3) colitis, and permanently discontinue pembrolizumab for life-threatening (Grade 4) colitis.

Immune-mediated hepatitis

Monitor subjects for changes in liver function (at the start of treatment, periodically during treatment and as indicated based on clinical evaluation) and symptoms of hepatitis, and exclude other causes of hepatitis. Administer corticosteroids (initial dose of 0.5 – 1.0 mg/kg/day for grade 2 events, and 1 – 2 mg/kg/day for grade 3 or greater events, of prednisone or equivalent, followed by a taper) and, based on severity of liver enzyme elevations, withhold or discontinue pembrolizumab.

Immune-mediated nephritis

Monitor patients for changes in renal function and exclude other causes of nephritis. Administer corticosteroids for grade 2 or greater events (initial dose of 1 – 2 mg/kg/day prednisone or equivalent, followed by a taper), withhold pembrolizumab for moderate (Grade 2), and permanently discontinue pembrolizumab for severe (Grade 3) or life-threatening (Grade 4) nephritis.

Immune-mediated endocrinopathies

Monitor subjects for signs and symptoms of hypophysitis (including hypopituitarism and secondary adrenal insufficiency) and exclude other causes of hypophysitis. Administer corticosteroids to treat secondary adrenal insufficiency and other hormone replacement as clinically indicated, withhold pembrolizumab for moderate (Grade 2), withhold or discontinue pembrolizumab for severe (Grade 3) or for life-threatening (Grade 4) hypophysitis.

Monitor subjects for hyperglycemia or other signs and symptoms of type 1 diabetes. Exclude other causes of diabetes. Administer insulin for type 1 diabetes, and withhold pembrolizumab in cases of severe hyperglycemia until metabolic control is achieved.

Thyroid disorders have been reported in subjects receiving pembrolizumab and can occur at any time during treatment; therefore, monitor subjects for changes in thyroid function (at the start of treatment, periodically during treatment and as indicated based on clinical evaluation) and clinical signs and symptoms of thyroid disorders. Hyperthyroidism may be managed symptomatically. Withhold pembrolizumab for severe (Grade 3) hyperthyroidism, and permanently discontinue pembrolizumab for life-threatening (Grade 4) hyperthyroidism. Hypothyroidism may be managed with replacement therapy without treatment interruption and without corticosteroids. For subjects with severe (Grade 3) or life-threatening (Grade 4) endocrinopathy that improves to Grade 2 or lower and is controlled with hormone replacement, continuation of pembrolizumab may be considered.

Other immune-mediated AEs

The following additional clinically significant, immune-mediated adverse reactions were reported in less than 1% (unless otherwise indicated) of subjects treated with pembrolizumab: uveitis, myositis, Guillain-Barré syndrome, pancreatitis and severe skin reactions (1.1%).

In addition, a set of irAEs have also been classified as immune-related events of clinical interest (irECI) a full list of these can be found in Table 12 in section 8.5.2. Patients with symptomatic irECIs should immediately stop receiving pembrolizumab and be evaluated to rule out non-treatment related causes of the event. Overdose and liver toxicity irECIs irrespective of relationship to the study drug should be reported within 24 hours of the investigator being aware to the Sponsor (via RM-CTU) who will in turn notify MSD. If the irECI is determined to be associated please refer to Appendix 5 for the recommendations on the management of these irECIs. If the event is not considered to be associated with the study drug the physician should exercise individual clinical judgment on the event management based on the patient. Any additional questions of the collection or information on management of irECIs should be directed to the Sponsor (via RM-CTU).

